#### **10.4.5 Safety observations**

Being this an observational study in which any prescription is by free physician's choice in accordance with the drug's technical data sheet, all safety information will be handled by the attending physician according to the local procedures. Since, however, events may occur, which are not endpoints but may imply the termination of the follow-up, these events will be tabulated by sub-population and/or individual medication, without additional statistical considerations.

### **11. Committees**

The Promoter will setup the Committees listed at continuation, to ensure the correct execution of the study and the respect of the subjects' rights.

#### **11.1 Steering Committee**

The study will be guided and monitored by a Steering Committee. The members of the Steering Committee are listed in § 3.1 above.

The Steering Committee has the responsibility of:

- a. supervising the progress of the study and ensuring that the protocol is carefully followed by every participant. To exert this responsibility the Steering Committee may appoint Monitors and, in such a case, is informed of all monitoring activities and, in particular, of the reports of the Data Monitoring and Safety Board (§ 3.2.3).
- b. proposing Protocol Amendments to solve, clarify and implement possible doubts, questions, or practical difficulties that may arise during the study, or that may become necessary owing to the scientific progress in the specific therapeutic field, to ensure that the scientific validity of the study is maintained.

- c. resolve doubts as to the classification of outcomes, if the need arises. To this aim, the individual subject's data supplied to the Committee will be anonymous as to the subject and to the Center, and blinded as to the applied treatment, if any.
- d. resolve doubts as to the protocol violation, if any, deciding whether the possible violation is to be considered a minor deviation, a major deviation, or a true violation, and whether the case has to be included into the ITT dataset (no other dataset is planned in this study). To this aim, the individual subject's data supplied to the Committee will be anonymous as to the subject and to the Center, and blinded as to the applied treatment.
- e. participate in the Writing Committee.

The Steering Committee appointed a Core Team of five persons, including a statistician. The Core Team has the responsibility of:

- a. managing the study according to the needs that may arise, and reports to the whole Steering Committee as needed;
- b. presenting to the Steering Committee a yearly report on the status of the trial, including the clinical results that may arise, until the closure of the study, which will incorporate the conclusions of the DMSB evaluation. The term "yearly" should be intended as the time at which the data relevant to the end-of-observation-year visit on the last subject recruited have been recorded and validated. Consequently, there will be one interim report; the second report coincides with the final study report.

The components of the Core Team are listed in § 3.1 above.

## 11.2 Writing Committee

The Writing Committee is composed of the Steering Committee and additional investigators if needed, based primarily on number of subjects enrolled and secondarily by speed of recruitment. The Writing Committee is led by the Core Team.

The Writing Committee has the responsibility of:

- a. preparing the main publication of the study results;
- b. deciding on additional and subsequent publications of planned and unplanned study results;
- c. requesting additional statistical analyses of the study data, in relation to the publications indicated above;
- d. defining the list of authors to each publication;
- e. managing the contacts with the Journals and the requests for clarification and modifications to the submitted papers.

## 11.3 Data Monitoring and Safety Board

The study shall be supervised by a specifically set-up DMSB.

The main purpose of the DMSB is to protect subjects, primarily those included in the trial but also other subjects with the disease in question. The second responsibility of the DMSB is to ensure the integrity of the study, in particular in the form of compliance with the procedures indicated in the protocol to ensure the data credibility.

The DMSB will be composed of three members including a statistician. The members of the DMSB should not be enrolling subjects into the study.

The DMSB has also the responsibility to recommend to the Steering Committee changes in the conduct of the study, whenever changes of clinical practice or information gathered in the study or in other ongoing studies suggest that the current conduct might have negative effects on the subjects' wellbeing.

The decision of the DMSB will be taken on data collected at the end of every year of long-term follow-up (i.e., when the last subject to be observed has completed the observation at the end of a full year).

Since there will be a total of 2 analyses of the endpoints monitored during the follow-up (one interim and one final), to maintain the overall alpha error at 0.05, the final analysis of these endpoints will report as statistically significant at the 95% level of confidence, P-values  $\leq 0.048$ .

## **12. Plans for disseminating and communicating study results**

This study will be registered at "[www.clinicaltrials.gov](http://www.clinicaltrials.gov)". Results will be disclosed in a publicly available database within the standard timelines.

The results of this observational study are intended to be published in a peer-reviewed journal and as abstracts/presentations at medical congresses under the oversight of the Promoter. Current guidelines and recommendation on good publication practice will be followed (e.g. STROBE [8]). To retain the integrity of the multicenter study, no individual investigator may publish on the results of this study, or their own subjects, or their country's subjects, without prior coordination with the Promoter.

## Appendix IV – CRF template

### BASELINE FORM 1/8

#### Identification

Centre:  _ _ _  (from system based on user/ password)	Consecutive number in the centre:  _ _ _  ID (from system)  _ _ _ _ _ _ _	
NOTE: if >40 issue warning		
Date of this visit (dd/mm/yyyy):  _ _ / _ _ / _ _ _		
Informed consent signed:  0-no [STOP] 1-yes	Consent date (dd/mm/yyyy):  _ _ / _ _ / _ _ _  [consent date must be <= date of visit]	
Date of birth:  _ _ / _ _ / _ _ _  (dd/mm/yyyy)	Age:  _ _ _  [computed by system; consent minus birth; must be >=18 years]	
Ethnicity:  1-White 2-Black 3-Asian 4-Latino 5-Native American (both North and South) 6-Arabic 7-Other (specify) 9-N/A	Specification: ..... [if Ethnicity=7]	Sex:  0-Female 1-Male 9-N/A

#### Index episode of venous thromboembolism

Date of diagnosis:  _ _ / _ _ / _ _ _  (dd/mm/yyyy) [must be 90-360 days before consent]	Type of event:  (only one option among: 1=proximal or proximal plus distal DVT of lower limbs 2=isolated distal DVT of lower limbs 3=DVT of lower limbs plus pulmonary embolism 4=pulmonary embolism without deep vein thrombosis
--	---

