### 7.2 Objectives

#### 7.2.1 Primary objective

The primary objective of the study is the assessment of the distribution of decisions on the modality to manage the secondary prevention of venous thromboembolism (VTE), at the end of the period of anticoagulation considered standard. This period, initiated after the index event and defined in the present protocol as maintenance anticoagulation, ranges from the end of the 3rd month to the end 12th month. The anticoagulant used for the maintenance anticoagulation may or may not be the same used in the initial acute phase of VTE management (the initial 7 days). To the effect of this study, the treatment applied during the acute phase is of no interest.

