## 8.2 Study set-up

### 8.2.1 Eligibility

Approximately 3,200 subjects will be enrolled. Each center will recruit not more than 40 among the consecutive subjects coming to the observation after approval of the protocol by the relevant EC/IRB until the total planned number of cases is overall collected. Consecutiveness may be replaced by other mean of bias containment if necessary given the center operational structure (e.g., all consecutive subjects reporting each first week of the month, a definite day in the week, or similar provisions). The selected predefined modality of screening and including patients should be declared by the participant centers. The subjects shall be able and willing to issue the informed consent to confer their data. Male and female adult and elderly subjects of any ethnicity, having had a first-ever event of DVT of the lower limbs and/or PE, treated with anticoagulants according to the local procedures but for not less than 3 and not more than 12 months, and having reached the final decision point on the therapy, are eligible to enter the study.

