#### **1. Enrollment and baseline visit**

The enrollment and baseline visit is the normally planned visit in which the physician has to decide on the continuation of the secondary prophylaxis after a first-ever thromboembolic episode treated for an appropriate period with anticoagulants. Due to organizational reasons, the enrollment and baseline visit may occur after the conclusion of anticoagulation. The time interval between conclusion of anticoagulation and enrollment visit should not exceed one month.

At the enrollment visit, all candidate subjects will receive an information sheet explaining design and aims of the study. The clinician shall explain and ask the subject to sign the informed consent form to confer the study data. The consent will also include the subject's agreement to receive regular phone calls from the investigator during the follow-up and to report annually to the center. The consent form will be part of the center documents and the only information conferred to the database will be whether the consent was signed or not, and in which date. The investigator will be responsible to archive the signed form for possible verification.

Subsequently, the investigator will:

- verify the inclusion/exclusion criteria for entering the study;
- inform by fax/mail the study Promoter that a new subject has been enrolled according to the protocol (form in Appendix III);
- obtain the information on the index event;
- monitor the clinical condition of veins and record the Villalta score;
- record the vascular risk factor, the concurrent diseases and the medications on long-term use;
- record the minimum clinical information required (weight, height, blood creatinine) as available; for creatinine, the last known serum creatinine level not older than three months before entering the study is appropriate;
- record the maintenance anticoagulation treatment received;
- decide on the subsequent subject's management and record the decision; the decision should be taken in the exclusive subject's interest and based exclusively on the personal judgment and in accordance with the local procedures;
- record the new form of management, if any;
- record the reasons influencing the decision taken;

- instruct the subject on the procedures of the follow-up, which should be the normal procedures in use at the center;
- provide a contact reference and obtain a contact reference.

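### The e-CRF limit of 360 days from index diagnosis to consent is 30 to 37 days shorter than the interval the protocol permits

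*Combined protocol and SAP*

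**What the plan says.** The baseline form in Appendix IV (Index episode of venous thromboembolism) places a range check on the date of diagnosis: it "must be 90-360 days before consent".

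Three statements in the protocol body govern the same interval:

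- **Treatment duration.** Section 8.2.1 makes subjects eligible if treated with anticoagulants according to local procedures, "but for not less than 3 and not more than 12 months". Section 7.2.1 says the maintenance period, started after the index event, "ranges from the end of the 3rd month to the end 12th month".
- **Delay to enrolment.** Section 8.3.1 (Enrollment and baseline visit) says: "Due to organizational reasons, the enrollment and baseline visit may occur after the conclusion of anticoagulation". It then sets the limit: "The time interval between conclusion of anticoagulation and enrollment visit should not exceed one month".
- **Timing of consent.** The same section puts consent at that visit: "The clinician shall explain and ask the subject to sign the informed consent form to confer the study data".

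The 90 to 360 day rule is not among the inclusion or exclusion criteria (sections 8.2.2 and 8.2.3). It appears only in the CRF template, and nothing elsewhere in the documents widens it.

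**The concern.** The check measures diagnosis to consent. Because consent is taken at the enrolment visit, any delay between the end of anticoagulation and that visit counts towards the interval. The check's limits match the 3 to 12 month treatment period alone and leave no room for the delay that section 8.3.1 grants. Yet the same form (Baseline form 6/8) lists resuming treatment among the options at the visit, which suggests that its authors expected some subjects to arrive with anticoagulation already stopped.

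The primary endpoint is the distribution of physicians' decisions among subjects taken consecutively or by another predeclared scheme. The records that fail the check are not a random subset. They belong to subjects treated for close to a year, most of them enrolled after treatment ended. If the check blocks entry, subjects who comply with the protocol could not be recorded. If it only queries, sites would be asked to justify or correct dates that are right.

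**Working it through.** **Inputs**

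- Check on diagnosis to consent: 90 to 360 days (Appendix IV, Baseline form 1/8).
- Anticoagulation: 3 to 12 months (sections 7.2.1 and 8.2.1).
- Delay from end of anticoagulation to enrolment: up to 1 month (section 8.3.1).
- Consent: at the enrolment visit (section 8.3.1).
- Assumption: treatment starts on the day of diagnosis.

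**Step 1. Reproduce the check.** 3 × 30 = 90 and 12 × 30 = 360. The stated limits are the treatment window in 30-day months, with nothing added.

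**Step 2. Add the permitted delay, 30-day months.** 12 × 30 + 30 = 390 days, and 390 − 360 = 30 days short.

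**Step 3. Repeat in calendar months,** over all 1,461 start dates in a four-year cycle.

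- 12 months is 365 to 366 days. With no delay this already exceeds the limit by 365 − 360 = 5 to 366 − 360 = 6 days.
- 12 months plus 1 month is 393 to 397 days. The excess is 393 − 360 = 33 to 397 − 360 = 37 days.

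**Step 4. Find who fails.** With a delay of L days, the latest end of treatment that still passes is day 360 − L after diagnosis:

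- L = 0: day 360
- L = 7: day 353
- L = 14: day 346
- L = 30: day 330, which is 330 / 30 = 11 months

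So only subjects treated for roughly 11 to 12 months can be caught, and how early the failure begins depends on the delay.

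**Step 5. Sensitivity to the start of the count.** If the 12 months ran from the end of the 7-day acute phase instead, the shortfall would be 30 + 7 = 37 days in 30-day months, or 33 + 7 = 40 to 37 + 7 = 44 days in calendar months. A later start of treatment can only enlarge the gap.

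**Step 6. Lower limit.** The delay does not affect it. Three calendar months is 89 to 92 days, so 90 is at most one day out. That is rounding and needs no change.

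**Step 7. Block or query?** The template uses three kinds of rule. A missing consent signature carries an explicit stop marker. Several other checks are explicitly a warning or a request for confirmation, for example on the number of subjects per centre: "NOTE: if >40 issue warning". The diagnosis-date rule carries neither marker. Nor does the age rule, which is worded in a similar way: "consent minus birth; must be >=18 years". The behaviour of this unmarked group is not stated.

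**The case against.** **A reader might infer that the check is a hard stop that shuts eligible patients out.** The mandatory wording, shared with the age limit, points that way. But the template has an explicit marker for a true block and does not use it here. It also implements a firm protocol limit, 40 subjects per centre, as a warning only. The appendix is a template, and section 8.5 refers to a database manual that is not among the documents. The hard-stop reading is therefore not established. Neither is its consequence, that follow-up could not be entered because the follow-up form requires a baseline form.

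**A reader might also infer a biased primary result.** The documents give no distribution of treatment durations or enrolment delays, so no shift in the proportions can be calculated. There are also central routes for recorded data: plausibility checks (section 8.5), Steering Committee rulings on deviations (section 11.1, item d) and exclusion only for major, irreconcilable deviations (section 10.3). None of them names this check or removes the contradiction, but they do make a serious effect less likely.

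**The 360 days could be a deliberate overall cap.** The delay is an exception for organisational reasons, and the inclusion criterion in section 8.2.2 says only that treatment usually lasts 3 to 12 months. This is possible, but sections 8.2.1 and 8.3.1 do not state such a cap. As written, they admit subjects whom the check rejects.

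**Simply raising the limit would create the opposite error.** This stands. Because the check does not measure treatment duration, a limit of 13 months would silently pass a subject treated for 13 months with no delay, contrary to section 8.2.1. The maintenance-treatment fields of the form are not visible in the available text, so a separate duration check may already exist.

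**Conclusion.** The contradiction holds. The check's upper limit is 30 days short in 30-day months and 33 to 37 days short in calendar months, counting treatment from the day of diagnosis. It fails subjects who meet the protocol window, including anyone enrolled at a full 12 calendar months with no delay.

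The conclusion goes no further than that. The documents do not show that the check blocks records, that patients are refused, or that the primary proportions move. The number of subjects affected is not derivable and may be small. The point merits correction because a stated data rule disagrees with the stated design and the correction is cheap.

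**What to change.** Reconcile the diagnosis-date check in Appendix IV with sections 7.2.1, 8.2.1 and 8.3.1, in one of two ways.

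- **If the protocol window is intended:** let the diagnosis-to-consent check cover 12 calendar months plus the one-month interval, calculated from the dates. Have values outside it raise a query and not a block; a short gap between diagnosis and start of treatment is then handled as well. Add separate checks on the duration of maintenance anticoagulation, which section 8.3.2 (item d) already lists as collected, and on the interval from its end to enrolment. The wider limit then cannot pass treatment beyond the 12 months in section 8.2.1 unnoticed.
- **If 360 days from diagnosis to consent is intended:** state it in sections 8.2.1 and 8.3.1.

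In either case, state in the CRF specification whether the check blocks or queries, and report the number of subjects outside the window.

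The cost is small edit-check changes, or a sentence in each of two sections, plus one count in the report. There are no extra patient procedures and no change to the analysis. If the end date of anticoagulation cannot be obtained from fields already on the form, one date field would be needed; the available text does not settle this.

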#### IN CASE OF DEEP VEIN THROMBOSIS:

location of the index episode:

(select all what applicable)

[only if type=1, 2 or 3;

at least one must be checked;

if both right and left are checked, request

confirmation]

[0=no; 1=yes]

VEIN	.....	left	.....	right
external iliac	.....		.....	
common femoral	.....		.....	
superficial femoral	.....		.....	
deep femoral	.....		.....	
popliteal	.....		.....	
posterior tibial	.....		.....	
peroneal	.....		.....	
anterior tibial	.....		.....	
medial gastrocnemius	.....		.....	
lateral gastrocnemius	.....		.....	
soleal	.....		.....	
saphenous (great and/or small)	.....		.....	

**BASELINE FORM 2/8****Index episode of venous thromboembolism  
additional information**

Superficial vein thrombosis:	 0-no 1-yes
In case of pulmonary embolism: Recent ( $\leq$ 1 month) echocardiography:	 If yes: date  _ / _ / _ _ _  0=no/1-yes – is NA with date blank if Type of event = 1 or 2
Signs of pulmonary hypertension:	 0=no/1-yes – is NA with date blank if Type of event = 1 or 2
HELP BOX: "PULMONARY HYPERTENSION"	

**THE INDEX EVENT WAS ASSOCIATED WITH:**

surgery	 0-no; 1-yes
severe trauma	 0-no; 1-yes
cancer	 0-no; 1-yes
motor function impairment (paraplegia)	 0-no; 1-yes
limb immobilization in the 3 months before the event	 0-no; 1-yes
central venous catheter	 0-no; 1-yes
chronic inflammatory disease	 0-no; 1-yes
bed rest >4 days	 0-no; 1-yes
pregnancy	 0-no; 1-yes; 9-N/A
puerperium	 0-no; 1-yes; 9-N/A
obesity	 0-no; 1-yes
heart failure	 0-no; 1-yes
nephrotic syndrome	 0-no; 1-yes
thrombophilia	 0-no; 1-yes;
polycythemia/thrombocythemia	 0-no; 1-yes
antiphospholipid antibody	 0-no; 1-yes
estrogens and/or progestins	 0-no; 1-yes
atrial fibrillation	 0-no; 1-yes
inferior vena cava filter	 0-no; 1-yes
long travel (> 4 h)	 0-no; 1-yes
other (specify)	 0-no; 1-yes
other; specification	.....

The index thromboembolic event was:	 idiopathic	 secondary
(only one choice; radio-button type)		

## HELP BOX PULMONARY HYPERTENSION – FOR DATABASE USE ONLY

### Echocardiographic probability of pulmonary hypertension in symptomatic patients with a suspicion of pulmonary hypertension

Peak tricuspid regurgitation velocity (m/s)	Presence of other echo 'PH signs' [a]	Echocardiographic probability of pulmonary hypertension
≤2.8 or not measurable	No	Low
≤2.8 or not measurable	Yes	Intermediate
2.9–3.4	No	
2.9–3.4	Yes	High
>3.4	Not required	

PH = pulmonary hypertension

[a] see table below

### Echocardiographic signs suggesting pulmonary hypertension used to assess the probability of pulmonary hypertension in addition to tricuspid regurgitation velocity measurement

A: The ventricles [a]	B: Pulmonary artery [a]	C: Inferior vena cava and right atrium [a]
Right ventricle/ left ventricle basal diameter ratio >1.0	Right ventricular outflow Doppler acceleration time <105 msec and/or midsystolic notching	Inferior cava diameter >21 mm with decreased inspiratory collapse (<50 % with a sniff or <20 % with quiet inspiration)
Flattening of the interventricular septum (left ventricular eccentricity index >1.1 in systole and/or diastole)	Early diastolic pulmonary regurgitation velocity >2.2 m/sec	Right atrial area (end-systole) >18 cm 
	PA diameter >25 mm.	

PA = pulmonary artery

[a] Echocardiographic signs from at least two different categories (A/B/C) from the list should be present to alter the level of echocardiographic probability of pulmonary hypertension.

Ref: The Joint Task Force for the Diagnosis and Treatment of Pulmonary Hypertension of the European Society of Cardiology (ESC) and the European Respiratory Society (ERS) Endorsed by: Association for European Paediatric and Congenital Cardiology (AEPC), International Society for Heart and Lung Transplantation (ISHLT). 2015 ESC/ERS Guidelines for the diagnosis and treatment of pulmonary hypertension. *European Heart Journal* 2016; **37**, 67-119. doi:10.1093/eurheartj/ehv317

## BASELINE FORM 3/8

### Clinical condition of veins

Recent ( $\leq 1$  month) compression ultrasound:  0-no  
 1-yes If yes: date | | | / | | | / | | | |

Extent of residual thrombosis:  
 (mark all locations with extent  $\geq 40\%$  of diameter or 4 mm):  
 0-no; 1-yes; default=no; if all=no and ultrasound=yes, ask confirmation

**LOCATION** ..... **left** ..... **right**  
 external iliac .....  .....   
 groin .....  .....   
 middle of thigh .....  .....   
 popliteal area .....  .....   
 distal deep veins .....  .....

Presence of:

varicose veins:	 0-absent; 1-present; default: absent
post-thrombotic syndrome:	 0-absent; 1-present; default: absent
oedema:	 0-absent; 1-present; default: absent
lipodermatosclerosis:	 0-absent; 1-present; default: absent
ulcer:	 0-absent; 1-present; default: absent

[check: if ulcer present, PTS must be present]

Villalta score:

Symptom/clinical signs default: 0	none	mild	moderate	severe
	=0	=1	=2	=3
Symptoms				
pain				
cramps				
heaviness				
paresthesia				
pruritus				
Clinical signs				
pretibial edema				
skin induration				
hyperpigmentation				
redness				
venous ectasia				
pain on calf compression				

Total score: | | | [computed from system: sum of all the above marks; ranges 0 to 33]

[system computes and stores classification of PTS; absent if 0-4; mild if 5-9; moderate if 10-14; severe if 15 or more or if ulcer from previous box is marked present]

[check: if Villalta  $\geq 5$  and post-thrombotic syndrome is marked absent, issue a warning]

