## 10.3 Populations

As usual in the observational studies, the analyses will be performed on the total sample monitored. Only subjects specifically indicated by the Steering Committee as major, irreconcilable deviation will be excluded from analysis (§ 11.1). Missing data will not be replaced. Subgroup analyses are not anticipated, however – given the exploratory nature of the study – unplanned subgroups analyses may be performed *post-hoc*, upon indications by the Steering Committee.

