**Current medications (used for at least 3 months) at this visit**

ASA <250 mg/day .....		0-no; 1-yes [default=no]
Other antiplatelets .....		
Antiarrhythmic agents .....		
Antidiabetics .....		
Antidyslipidemic agents .....		
ACE inhibitors .....		
Sartans .....		
Beta-blockers .....		
Diuretics .....		
Calcium antagonists .....		
Other antihypertensive agents .....		
Nitrates .....		
Digitalis .....		
Proton pump inhibitors .....		
Antiviral agents .....		
Immunosuppressives .....		
Steroids .....		
Drugs for thyroid disorders .....		
Analgesic agents .....		
Anti-inflammatory drugs .....		

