## Events occurred after last interview

[check: if any left box is marked "yes", there MUST be a right box marked "yes" or date/reason]

Thrombotic complications:	 0-no	if yes, specify:	deep vein thrombosis pulmonary embolism superficial vein thrombosis transient ischemic attack (TIA) ischemic stroke acute myocardial infarction sudden/cardiac death other; specify	 0-no; 1-yes; default=no        [CHECK death below]
[text]				
Bleeding complications:	 0-no; 1-yes; default=no	
 _ _  0; if bleeding complication=yes, should be <math>\geq 1</math>
 
 major bleeding  clinically relevant non-major bleeding  other bleeding
 
N/A; if bleeding complication = yes, at least one should be indicated
 
HELP BOX BLEEDING CLASSIFICATION
		
if yes, specify how many:				
if yes, specify:		type of complication:		

if yes, specify the nature of the complication:
 
cerebral hemorrhage/hemorrhagic stroke gastrointestinal hemorrhage retroperitoneal hemorrhage intra-ocular hemorrhage retinal bleeding intra-articular hemorrhage (hemarthrosis) hemoglobin drop by 2 or more g/dL transfusion of 2 or more units of red cell concentrate uterine bleeding skin/muscle hematoma nose bleed bleeding gums anal bleeding other; specify
				
[text]				
Hospitalization:	 0-no  1-yes	if yes, specify:	date (dd/mm/yyyy)  _ _ / _ _ / _ _ _ _	[text]
Patient's death:	 0-no  1-yes	if yes, specify:	date (dd/mm/yyyy)  _ _ / _ _ / _ _ _ _	
Any other event preventing continuation of the follow-up	 0-no  1-yes	if yes, specify:	date (dd/mm/yyyy)  _ _ / _ _ / _ _ _ _	[text]
		reason:	_ _ _ _ _ _ _ _ _ _	

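### Baseline form 3/8 stores unscanned residual thrombosis, unscored Villalta items and unexamined vein signs as negative findings

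*Combined protocol and SAP*

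**What the plan says.** Baseline form 3/8 (Appendix IV, Clinical condition of veins) first asks whether a compression ultrasound was done within the last month, yes or no, with a date. It then lists five locations on each side for residual thrombosis, coded "0-no; 1-yes; default=no; if all=no and ultrasound=yes, ask confirmation".

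Below that, varicose veins, post-thrombotic syndrome (PTS), oedema, lipodermatosclerosis and ulcer are each coded "0-absent; 1-present; default: absent". The Villalta grid of five symptoms and six clinical signs carries "Symptom/clinical signs default: 0". Its total is "computed from system: sum of all the above marks; ranges 0 to 33", and the system stores a PTS class from it: absent for 0 to 4, with higher classes from 5 upward or, for severe, when an ulcer is marked.

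Two cross-checks are printed. A marked ulcer requires PTS to be present. If the total is 5 or more "and post-thrombotic syndrome is marked absent, issue a warning".

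Section 8.3.2 (c) lists the condition of the veins and the Villalta score among the prognostic variables. Section 10.4.2 allows prognostic factors to be tested against the decision by chi square or logistic regression. Section 10.3 states: "Missing data will not be replaced".

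**The concern.** A pre-filled negative makes two different states look the same: examined and found negative, and not examined. None of the fields above has a code for the second state. The same CRF does provide one elsewhere. Pulmonary hypertension on form 2/8 becomes NA when the index event was DVT only, and the thrombophilia test under Vascular risk factors has a not-done code.

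Some non-assessment is foreseeable for residual thrombosis. The study adds no procedures to routine care (Sections 8.3 and 9.1), and ultrasound is itself a yes/no item. Subjects whose index event was pulmonary embolism without DVT are eligible, and no branch takes them past the vein fields.

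At stake are the descriptive prevalence of these findings and their association with the decision. If centres or countries differ in how often they scan, they would also differ in recorded prevalence when the true prevalence is the same. The primary endpoint, the decision itself, is not affected.

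**Working it through.** The plan gives no figure for the share of subjects not scanned or not scored, so there is no stated result to reproduce. The check has two parts.

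**1. Which untouched entries would be caught?**

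- *Residual thrombosis, ultrasound = yes, all locations 'no'.* Confirmation is requested, so a scanned negative is actively verified.
- *Residual thrombosis, ultrasound = no.* No query is raised and ten 'no' values (5 locations × 2 sides) are stored. The ultrasound field still identifies these subjects.
- *Villalta.* 11 items × maximum 3 = 33, which matches the printed range. An untouched grid gives 11 × 0 = 0 and, with ulcer also untouched, PTS class 'absent'. The warning needs a total of 5 or more and cannot fire. The separate PTS item also defaults to absent, so the two defaults agree with each other.
- *Five vein signs.* The only check starts from a marked ulcer, so untouched 'absent' entries pass.

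A database review for completeness (Section 8.5) would see all of these fields as filled.

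**2. Size for residual thrombosis if the ultrasound field is ignored**

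Assumptions, none of them from the documents:

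- true prevalence of residual thrombosis 0.40;
- probability of extended anticoagulation 1/2 with it and 1/3 without it, so the true odds ratio (OR) is 1 / 0.5 = 2.0;
- a share u not scanned, at random.

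Recorded 'yes': 0.40(1 − u), with odds of extended anticoagulation 1.

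Recorded 'no': 0.60 + 0.40u. Of these, 0.60/3 + 0.40u/2 = 0.2 + 0.2u receive extended anticoagulation and 0.4 + 0.2u do not.

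Recorded OR = 1 ÷ [(0.2 + 0.2u)/(0.4 + 0.2u)] = (2 + u)/(1 + u).

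| u | Recorded prevalence | Recorded OR |
|---|---|---|
| 0.3 | 0.40 × 0.7 = 28% | 2.3/1.3 = 1.77 |
| 0.5 | 0.40 × 0.5 = 20% | 2.5/1.5 = 1.67 |
| 0.6 | 0.40 × 0.4 = 16% | 2.6/1.6 = 1.63 |

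Restricted to scanned subjects, prevalence is 0.40(1 − u)/(1 − u) = 40% and the OR is 2.0. Under these assumptions, using the field removes the whole bias.

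If scanning depends on the intended decision, the at-random assumption fails. The recorded OR can then move in either direction, and restriction is no longer guaranteed to be unbiased.

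No comparable figure is offered for Villalta or the vein signs, because nothing in the documents indicates how often they would be left unscored.

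**The case against.** The strongest reply is that little is lost. The ultrasound field acts as a not-assessed code for residual thrombosis, and a careful analyst would use it. That stands: the odds ratios above describe an avoidable analysis, not an inevitable one. What remains is that no rule tells the analyst to do so.

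Second, recording the Villalta score is a listed task of the enrollment visit (Section 8.3.1). Availability is a condition only for weight, height and creatinine, so an unscored grid would be a protocol deviation. This also stands, and it leaves the frequency unknown. But the default is what would hide such a deviation.

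Third, Section 8.5 refers to a database manual that is not among the documents, and its entry instructions may help. They could not make a stored 0 distinguishable from an untouched 0.

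Two stronger readings are tempting, and the documents support neither.

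- *Bleeding rates are biased downward.* The top-level bleeding box at follow-up does carry "0-no; 1-yes; default=no". However, bleeding is to be asked about at every contact (Synopsis; Section 8.3.1), and the default acts only inside a form opened for a dated contact. A missed contact leaves no form, not a 'no'.
- *The defaults contradict the missing-data rule in Section 10.3.* That rule governs analysis and the defaults govern entry. The text contains no inconsistency. The practical effect is that an unassessed item never reaches the rule as missing.

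Negative defaults on the concurrent-disease list and the medication list ("0-no; 1-yes [default=no") are of less concern. Compulsory entry on every disease row would add work that is not clearly justified, and Section 8.1.3 already names staff time for data entry as a possible source of bias.

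**Conclusion.** The point holds as a data-capture flaw on Baseline form 3/8. For residual thrombosis it is recoverable. Its size, a recorded prevalence of 28% to 16% against 40% and an OR of 1.77 to 1.63 against 2.0, arises only if the ultrasound field is ignored, and it rests entirely on the assumed prevalence, odds ratio and 30% to 60% unscanned at random. For the 11 Villalta items and the five vein signs, an untouched entry cannot be told from a true negative afterwards, and the extent is unknown.

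The consequence is confined to descriptive and exploratory analyses (Section 10.1) of prognostic factors. No bias in bleeding rates is shown. The change is worth making because it is specific and cheap, and because the Villalta and vein-sign information cannot be rebuilt from the database later.

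**What to change.** - **Residual thrombosis:** set all ten location fields to N/A when ultrasound = no, using the logic that form 2/8 already applies to pulmonary hypertension. State in Section 10.4 that these fields are analysed only in scanned subjects, and report how many were scanned, by country.
- **Villalta and vein signs:** remove the defaults from these 16 fields (11 + 5) and add a not-assessed code. Compute the Villalta total and PTS class only when all 11 items are entered; otherwise leave both missing.
- **Bleeding box at follow-up:** as a minor precaution, print no default, as is already the case for the top-level thrombotic, hospitalization and death boxes.
- **If entry has already begun:** set residual thrombosis to missing for unscanned subjects, and query all-zero Villalta grids against the source documents.

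The cost is a small amount of e-CRF programming, a few more clicks per baseline form, and some openly missing values. Analyses of residual thrombosis will also rest on fewer subjects. Under the assumed 30% to 60% unscanned, that is 3,200 × 0.7 = 2,240 down to 3,200 × 0.4 = 1,280.
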